10.3. Data Analysis Considerations

10.3.1. Analysis Populations

The run-in population will consist of all subjects who took at least one dose of single-blind placebo dose during the run-in period.

The Randomized Safety Population will consist of all subjects who were randomized and took at least one dose of investigational product (i.e., nelotanserin or placebo) during the double-blind treatment phase.

The Full Analysis Set (FAS) will consist of all randomized subjects who took at least one dose of investigational product during the double-blind treatment phase, with evaluable baseline primary efficacy assessment, and a post-baseline primary efficacy assessment.

The Per-Protocol Analysis Set (PPAS) will consist of all subjects in the FAS who did not have any major protocol deviations.

10.3.2. Interim Analysis

No interim efficacy analyses are planned.

10.4. Key Elements of Analysis Plan

The primary objective of this study is to evaluate the efficacy of nelotanserin in reducing the nightly frequency of characteristic RBD behaviors (sum of simple/major and complex events per 10 minutes of REM sleep) following 4 weeks of treatment for patients with DLB.

Descriptive statistics for all efficacy and safety measures over the course of the study will be presented for the DLB patient subgroup, as well as for the PDD patient subgroup and the full patient sample. Continuous data will be summarized by means, standard deviations, standard errors, medians, interquartile ranges, maximum observed value, minimum observed value, and number of subjects. Categorical data will be summarized by frequency counts and proportions.

Listings will be sorted by subject and time. Summaries will be presented by treatment, disease type, and time. Version 9.2 or higher of the SAS system will be used to analyze the data as well as to generate tables, figures, and listings. Further details of analyses to be performed will be provided in the statistical analysis plan (SAP).

Analysis datasets will be constructed using version SAS 9.2 or later following current CDISC guidelines.

Missing data will not be imputed for primary analysis. If there are missing data at EOS visits for the primary or key secondary efficacy endpoints, the impact of missing data will be evaluated by testing the primary analysis model using the subset of the Randomized Safety Population who have an evaluable primary endpoint assessment at baseline, with any missing values at EOS imputed using multiple imputation. Details of imputation and any changes or refinements necessary will be documented in the SAP.

Compliance:

- Summary of treatment compliance will be presented by treatment arm. The number and percentage for compliance expressed as a categorical variable (<80%, ≥80% to ≤120%, and >120%) will also be presented by treatment arm.
- For efficacy endpoints derived based on the study diary, if subjects report values for < 50% of days during a weekly period, all daily values for that item (and thus all endpoints that are computed using that item) will be set to missing for that week.
- Efficacy endpoints assessed with ActiGraph will only be calculated for each weekly period during the run-in and double-blind treatment periods for subjects with non-missing data for at least 4 nights during that week.

10.4.1. Efficacy Analyses

For the primary efficacy endpoint, statistical significance of between-group differences in change in frequency per 10 minutes of REM sleep of RBD behaviors (sum of simple/major and complex RBD events) for the DLB patient subgroup and for the PDD patient subgroup, based on video/audio assessment conducted at a sleep laboratory from baseline to EOS, will be tested using univariate ANCOVA models that include treatment arm as a fixed effect and both baseline value and status (presence/absence) of background treatment with melatonin/clonazepam (or other benzodiazepines) as covariates.

For secondary and exploratory efficacy endpoints for which treatment comparisons of change in values will be compared across 2 time points (ie, baseline and EOS), statistical significance of between-group differences in change in mean values from baseline to EOS visits will be tested for the DLB patient subgroup, the PDD patient subgroup, and all patients using univariate ANCOVA models that include treatment arm as a fixed effect and both the baseline value of the endpoint and status (presence/absence) of background treatment with melatonin/clonazepam (or other benzodiazepines) as covariates. The models for all patients will also include disease type (DLB or PDD) and treatment arm by disease type interaction as fixed effects.

For CGIC-RBD, for which treatment comparisons of difference in values will be compared at EOS (V5/ET) only, statistical significance of between-group differences in mean values will be tested for the DLB patient subgroup, the PDD patient subgroup, and all patients using univariate ANCOVA models that include treatment arm as a fixed effect and baseline status (presence/absence) of background treatment with melatonin/clonazepam (or other benzodiazepines) as a covariate. The model for all patients will also include disease type (DLB or PDD) and the treatment arm by disease type interaction as fixed effects.

For secondary and exploratory efficacy endpoints for which treatment comparisons of change in values will be compared across multiple weeks (ie, Weeks 0, 1, 2, 3, and 4 for study diary and ActiGraph assessments), statistical significance of between-group differences in change in mean values across weeks will be tested for the DLB patient subgroup, the PDD patient subgroup, and all patients using MMRM models that include subject as a random effect, treatment arm as a between-subjects fixed effect, week as a repeated-measures fixed effect, treatment arm by week interaction as a fixed effect, and status (presence/absence) of background treatment with melatonin/clonazepam (or other benzodiazepines) as a covariate. The models for all patients will

also include disease type (DLB or PDD) and the treatment by disease type interaction as fixed effects. Degrees of freedom will be calculated using Satterthwaite's formula ([Satterthwaite, 1946](#)). An unstructured covariance matrix will be assumed for residuals.

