	
treatment with melatonin/clonazepam (or other benzodiazepines) as covariates. The models for all patients will also include disease type (DLB or PDD) and the treatment arm by disease type interaction as fixed effects.
 
For CGIC-RBD, for which treatment comparisons of difference in values will be compared at EOS (V5/ET) only, statistical significance of between-group differences in mean values will be tested for the DLB patient subgroup, the PDD patient subgroup, and all patients using univariate ANCOVA models that include treatment arm as a fixed effect and baseline status (presence/absence) of background treatment with melatonin/clonazepam (or other benzodiazepines) as a covariate. The model for all patients will also include disease type (DLB or PDD) and the treatment arm by disease type interaction as fixed effects.
 
For secondary and exploratory efficacy endpoints for which treatment comparisons of change in values will be compared across multiple weeks (ie, Weeks 0, 1, 2, 3, and 4 for study diary and ActiGraph assessments), statistical significance of between-group differences in change in mean values across weeks will be tested for the DLB patient subgroup, the PDD patient subgroup, and all patients using mixed-effects models for repeated measures (MMRM) that include subject as a random effect, treatment arm as a between-subjects fixed effect, week as a repeated-measures fixed effect, treatment arm by week interaction as a fixed effect, and status (presence/absence) of background treatment with melatonin/clonazepam (or other benzodiazepines) as a covariate. The models for all patients will also include disease type (DLB or PDD) and the treatment by disease type interaction as fixed effects. Degrees of freedom will be calculated using Satterthwaite's formula. An unstructured covariance matrix will be assumed for residuals.
 
Safety: Safety will be assessed by summarizing and analyzing AEs, laboratory analytes, vital signs, ECG parameters, physical examination findings, concomitant medications, and C-SSRS scores for all patients and separately for the DLB and PDD subgroups. Cognitive functioning as assessed with the MoCA and the MMSE will be also summarized.
 
Pharmacokinetics/Pharmacodynamics (PK/PD): Plasma nelotanserin and M1 metabolite concentrations will be listed and summarized by visit. Exploratory PK/PD analysis will include a plot of nelotanserin and M1 concentrations versus the change in nightly frequency of RBD behaviors from baseline to EOS.

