To assess the effects of nelotanserin versus placebo on both severity and frequency of RBD behaviors (sum of simple/minor, simple/major, and complex RBD events) in the DLB patient subgroup based on video/audio assessment conducted at a sleep laboratory	The change in the composite score based on both severity and frequency of RBD behaviors (sum of simple/minor, simple/major, and complex RBD events) from baseline (V3) to EOS (V5/ET) in the DLB patient subgroup
To assess the effects of nelotanserin versus placebo on the number of injuries to the subject or bed partner in the DLB patient subgroup as recorded on the study diary completed by the subject and/or bed partner/caregiver	The change in the number of nights with injurious behaviors to the subject or bed partner per week from baseline (Week 0) to EOS (Week 4) in the DLB patient subgroup
To assess the effects of nelotanserin versus placebo on presence, frequency and severity of sleep behaviors in the DLB patient subgroup as recorded on the study diary completed by the subject and/or bed partner/caregiver	The change in the number of nights with no sleep movements and/or vocalizations per week, the nightly number of sleep movements and/or vocalizations per week, the nightly severity of sleep movements and/or vocalizations per week, and a composite score based on nightly number and severity of sleep movements and/or vocalizations per week from baseline (Week 0) to EOS (Week 4) in the DLB patient subgroup.
To assess the effects of nelotanserin versus placebo on subjective sleep quality in the DLB patient subgroup based on scores from the Scales for Outcomes in Parkinson's disease (SCOPA) – Sleep	The change in SCOPA–Nighttime Sleep (NS) problems and Daytime Sleepiness (DS) subscale scores from baseline (V4) to EOS (V5/ET) in the DLB patient subgroup
To assess the effects of nelotanserin versus placebo on quality of bed partner sleep in the DLB patient subgroup as measured by a visual analog scale (VAS) completed by the bed partner	The change in quality of bed partner sleep as measured by a VAS completed by the bed partner from baseline (V4) to EOS (V5/ET) in the DLB patient subgroup
To assess the effects of nelotanserin versus placebo on clinicians' rating of change in RBD behaviors in the DLB patient subgroup as measured by Clinicians' Global Impression of Change in RBD Behaviors (CGIC-RBD)	The comparison of CGIC-RBD at EOS (V5/ET) in the DLB patient subgroup

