- The change in the mean EMG activity during REM sleep, based on PSG assessment conducted at a sleep laboratory, from baseline to EOS will be statistically equivalent for nelotanserin and placebo treatment arms for the DLB patient subgroup.
- The change in the mean number of nights with injurious behaviors to the subject or the bed partner per week, based on self or caregiver reports from the daily study diary, from baseline to EOS will be statistically equivalent for nelotanserin and placebo treatment arms

for the DLB patient subgroup.

- The change in the mean number of nights with no sleep movements per week, the mean nightly number of sleep movements per week, the mean nightly severity of sleep movements per week, and in the mean composite score based on nightly number and severity of sleep movements per week, based on self or caregiver reports from the daily study diary, from baseline to EOS will be statistically equivalent for nelotanserin and placebo treatment arms for the DLB patient subgroup.
- The change in the mean number of nights with no sleep vocalizations per week, the mean nightly number of sleep vocalizations per week, the mean nightly severity of sleep vocalizations per week, and in the mean composite score based on nightly number and severity of sleep vocalizations per week, based on self or caregiver reports from the daily study diary, from baseline to EOS will be statistically equivalent for nelotanserin and placebo treatment arms for the DLB patient subgroup.
- The change in mean SCOPA NS subscale scores from baseline to EOS will be statistically equivalent for nelotanserin and placebo treatment arms for the DLB patient subgroup.
- The change in mean SCOPA DS subscale scores from baseline to EOS will be statistically equivalent for nelotanserin and placebo treatment arms for the DLB patient subgroup.
- The change in mean VAS score for quality of bed partner sleep from baseline to EOS will be statistically equivalent for nelotanserin and placebo treatment arms for the DLB patient subgroup.
- The difference in mean CGIC-RBD score at EOS will be statistically equivalent for nelotanserin and placebo treatment arms for the DLB patient subgroup.

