- The change in objective sleep parameters assessed from PSG (including but not limiting to WASO; number of arousals; SE; TST; duration and proportion of sleep time in Stage 1, Stage 2, Stage 3, and REM; latency to sleep/persistent sleep; latency to Stage 1, Stage 2, Stage 3, and REM; duration of wakefulness) from baseline to EOS will be statistically equivalent for nelotanserin and placebo treatment arms for the DLB patient subgroup.
- The change in mean nightly total count assessment from the ActiGraph activity monitor from baseline to EOS will be statistically equivalent for nelotanserin and placebo treatment arms for the DLB patient subgroup.

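### The diary and ActiGraph repeated-measures model treats Week 0 as an unconstrained outcome, so its Week 4 effect is an unadjusted change score

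*Combined protocol and SAP*

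**What the plan says.** Section 10.4.1, repeated under Statistical Methods in Section 2, covers endpoints compared over several weeks: "Weeks 0, 1, 2, 3, and 4 for study diary and ActiGraph assessments". It specifies "MMRM models that include subject as a random effect, treatment arm as a between-subjects fixed effect, week as a repeated-measures fixed effect", plus arm-by-week and background-treatment status as a single covariate. It adds: "An unstructured covariance matrix will be assumed for residuals". No baseline value is listed, and the arm means are not constrained at Week 0. For the pooled sample: "The models for all patients will also include disease type (DLB or PDD) and the treatment by disease type interaction as fixed effects". Neither of those terms is crossed with week.

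The test is described only as "between-group differences in change in mean values across weeks will be tested". The contrast of interest comes from elsewhere. Section 4 defines the injury endpoint as nights "per week from baseline (Week 0) to EOS (Week 4) in the DLB patient subgroup", and the other diary endpoints and the ActiGraph endpoint use the same two weeks. Section 10.1 states hypotheses on "The change in mean nightly total count assessment from the ActiGraph activity monitor from baseline to EOS" and, for the diary, on changes "based on self or caregiver reports from the daily study diary, from baseline to EOS will be statistically equivalent".

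The same Section 10.4.1 adjusts every change endpoint measured at two time points for its own baseline value and for background status. Section 7.2 stratifies randomization by disease type and background treatment. Section 10.4 sets weekly completeness rules for both instruments and leaves further detail to an SAP; the supplied text specifies this model no further.

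**The concern.** One family of endpoints is adjusted for baseline and the other is not, with no reason given. If Week 0 is an outcome with free arm means, the change to Week 4 carries the full noise of the Week 0 measurement and any chance imbalance between arms. In a subgroup of about 34, that precision matters, and the data needed to recover it are already collected.

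The second issue is in the all-patients model. A treatment-by-disease term that is constant over weeks, in a model whose weeks include a pre-treatment one, does not measure whether the treatment effect differs between DLB and PDD. The term of the same name in the ANCOVAs does, so a reader could easily misread it.

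**Working it through.** **1. The plan's own figure.** Sections 2 and 10.2 give power 0.62 for the primary ANCOVA: 34 subjects, difference 0.8, SD 1, Cohen's f = 0.4, alpha 0.05, two covariates. With noncentrality 0.4² × 34 = 5.44 on 1 and 30 df, the noncentral F gives 0.617, so the figure reproduces. The plan gives no power for the diary or ActiGraph model. The 0.8 effect and 17 per arm are borrowed below only as a scale; the SDs and correlations are assumptions.

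**2. What the Week 4 contrast estimates.** Let b be the background coefficient. With complete data, each fitted arm-by-week mean is the raw arm mean for that week minus b times the arm's mean background status. The second part is the same at every week, so it drops out of Week 4 minus Week 0. What remains is the raw difference in mean change, whatever the covariance matrix. In the all-patients model the disease terms cancel in the same way. Generalized least-squares fits to 500 random data sets each for the DLB and all-patients models, with a background effect on change built in, agreed to below 1e-13.

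**3. Precision.** Let r be the Week 0 to Week 4 correlation and s the Week 0 SD divided by the Week 4 SD. With 34 subjects, the variance of the baseline-adjusted effect relative to the change score is

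(1 − r²) / (1 + s² − 2rs) × (1 + 1/30).

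For r = 0.5, s = 1: 0.75 / 1 × 1.033 = 0.78.

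| s | r = 0.3 | 0.5 | 0.7 | 0.9 |
|---|---|---|---|---|
| 0.75 | 0.85 | 0.95 | 1.03 | 0.92 |
| 1 | 0.67 | 0.78 | 0.88 | 0.98 |
| 1.25 | 0.52 | 0.59 | 0.65 | 0.63 |

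These figures adjust for baseline only. Any gain from background status is not included.

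**4. Power (two-sided 0.05, s = 1).** At r = 0.5 the change score has noncentrality 0.8 / √(1 × 2/17) = 2.33 on 32 df, giving 0.62. The adjusted analysis has 0.8 / √(0.75 × 1.033 × 2/17) = 2.65 on 31 df, giving 0.73.

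| Effect | r = 0.3 | 0.5 | 0.7 | 0.9 |
|---|---|---|---|---|
| 0.8 SD | 0.48 to 0.64 | 0.62 to 0.73 | 0.83 to 0.87 | no gain |
| 0.5 SD | 0.22 to 0.31 | 0.29 to 0.36 | 0.45 to 0.49 | 0.88 to 0.89 |

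**5. Missing Week 0.** Suppose 3 of 17 per arm have no usable Week 0 (equal SDs, exchangeable correlation). For r = 0.3, 0.5, 0.7, 0.9, the variance relative to the model as written is 0.59, 0.69, 0.80, 0.93 with arm means constrained at Week 0. With Week 0 as a covariate, which drops those subjects, it is 0.70, 0.81, 0.91, 1.02.

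**6. Treatment-by-disease.** The coefficient averages the DLB-PDD difference in arm effects over five weeks with weights Σ⁻¹1 / (1ᵀΣ⁻¹1). Assume an effect of −0.8 in DLB and 0 in PDD at Weeks 1–4, and none at Week 0. The true interaction is 0.80 and the expected coefficient is 0.80 × (1 − w₀), where w₀ is the Week 0 weight. With equal SDs and exchangeable correlation w₀ = 0.20, giving 0.64. With Week 0 SD 0.75 and r = 0.5, w₀ = 0.57, giving 0.34.

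| Week 0 SD | r = 0.3 | 0.5 | 0.7 | 0.9 |
|---|---|---|---|---|
| 0.75 | 0.46 | 0.34 | 0.10 | −0.66 |
| 1 | 0.64 | 0.64 | 0.64 | 0.64 |
| 1.25 | 0.74 | 0.80 | 0.94 | 1.47 |
| 1.5 | 0.79 | 0.87 | 1.04 | 1.52 |

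Under AR(1) with equal SDs it is 0.61, 0.57, 0.52, 0.45.

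**7. Random subject effect.** A random intercept adds nothing that an unstructured 5 × 5 matrix does not already contain. It may produce convergence warnings but does not alter the treatment test once the model fits.

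**The case against.** The strongest reply is that nothing here is wrong. Treating Week 0 as a response is a legitimate longitudinal model, its change contrast is unbiased, and it keeps subjects with no usable Week 0. All of that stands, and it is why the point concerns efficiency and the first-choice fix keeps Week 0 as a response.

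The raw-change identity is exact only with complete weekly data. With 15% of weekly values missing, the estimate differs from the complete-case raw change. That is correct, but missing data do not put a baseline adjustment into the model. Section 10.4.1 also names no Week 4 contrast, but an omnibus arm-by-week test would equally lack adjustment. Reading the outcome as change from baseline does not help: change at Week 0 would be identically zero and could not sit in an unstructured matrix.

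The size of the gain is unknown because it rests on assumed correlations and SDs; this stands. So does the point that no test of treatment-by-disease is announced, that the term drops out of the Week 4 change contrast, and that the wrong sign needs an extreme assumption.

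Finally, the constrained model can be anti-conservative in small samples. At 17 per arm its unadjusted model-based variance is about 6% too small and simulated type I error is 0.052 to 0.057. At an assumed 9 per arm, near the PDD subgroup (52 − 34 = 18), unadjusted error reached 0.061 to 0.082. This is the most serious objection. In two-time-point fits, Kenward-Roger brought it from 0.061–0.074 to 0.051–0.060 at 9 per arm and, at a correlation of 0.3, from about 0.060 to 0.055 at 17 per arm (simulation error about 0.005).

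**Conclusion.** The concern holds, as an avoidable loss of precision rather than a validity error. As written, the Week 4 treatment effect on the diary and ActiGraph endpoints is, with complete data, a raw change-score comparison in which the background covariate plays no part. Over the assumed range, baseline adjustment changes its variance by between a 48% reduction and a 3% increase. With equal SDs the reduction is 33% at a correlation of 0.3 and 2% at 0.9.

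The all-patients treatment-by-disease coefficient should not be read as a DLB-versus-PDD difference in effect. Depending on the covariance it can be too small, too large or, at one extreme, of the wrong sign. This matters only if someone reads it that way.

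Only other-secondary and exploratory endpoints are affected. The primary and key secondary ANCOVAs, and the 0.62 power figure, are untouched. The change is worth making because it is cheap and uses data already collected.

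**What to change.** In Section 10.4.1 and the matching synopsis text:

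- Keep Weeks 0–4 as outcomes, but constrain the arm means to be equal at Week 0, with treatment terms at Weeks 1–4 only.
- Cross background-treatment status with week, and keep the unstructured matrix.
- Name the Week 4 treatment contrast as the test.
- Use Kenward-Roger in place of Satterthwaite for this model.
- In the all-patients model, add disease-by-week and treatment-by-disease-by-week, and read any interaction at Week 4. Under four covariances tried, this recovered the true 0.80.
- Remove the random subject effect (tidying only).

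Second choice: Weeks 1–4 as outcomes, with the Week 0 value and its interaction with week as covariates. Simulated type I error at 17 per arm was 0.044 to 0.051, but subjects with no usable Week 0 are lost.

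The cost is wording, with no new data. The constrained DLB model has 14 fixed-effect and 15 covariance parameters (29), against 11 + 16 = 27 as written; the second choice has 13 + 10 = 23. The constrained all-patients model has 23 + 15 = 38, against 13 + 16 = 29. The remaining downside is slightly raised type I error in small subgroups, largely but not entirely removed by Kenward-Roger in the fits above.

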5. STUDY DESIGN

5.1. Overall Design

This is a multicenter, double-blind, randomized, placebo-controlled study in DLB or PDD subjects with RBD. The study will be conducted at approximately 25 sites.

[figure not shown]
Following an initial screening period, eligible subjects will be given ActiGraph activity monitors at run-in visit (V2) to wear nightly throughout the course of the study (including sleep laboratory nights), and subjects and their caregivers/bedpartners will record sleep behaviors on a diary throughout the study. Subjects will then enter a single-blind placebo run-in period of up to 30 days in duration during which baseline video-PSG will be obtained at a sleep laboratory (baseline/Visit 3). To allow subjects to be acclimated to the sleep laboratory environment, subjects will spend a minimum of 2 (preferably consecutive) nights at the sleep laboratory. To be eligible for randomization, the subject must have at least one qualifying night which is defined as a night with all of the following criteria met: 1) a total REM sleep duration ≥ 10 minutes based on PSG assessment, 2) at least 4 RBD events per 10 minutes of REM per night based on video/audio review, and 3) at least one simple/major or complex RBD event per night based on video/audio review. At the end of the single-blind placebo run-in period, all subjects who continue to meet the eligibility criteria will enter a 4-week double-blind treatment period. Each subject will be randomized 1:1 to either nelotanserin 80 mg or matching placebo. For subjects assigned to nelotanserin 80 mg, the dose will be titrated up to the 80-mg dose strength in a blinded fashion after initial 5 days of treatment with 40 mg nelotanserin. Subjects will be assessed for primary efficacy using a whole-night video-PSG for at least 2 nights at a specified sleep laboratory again after approximately 4 weeks of the double-blind treatment (end of study [EOS]/Visit 5).

Following the final visit, subjects who have completed the study may be eligible to participate in an open-label extension study with nelotanserin. The study design is outlined in [Figure 1](#) **Error! Reference source not found.**

The primary objective is to assess the effects of nelotanserin versus placebo on the frequency per 10 minutes of REM sleep of characteristic RBD behaviors (sum of simple/major and complex RBD events) for the DLB patient subgroup, based on video/audio assessment conducted at a sleep laboratory.

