6. SUBJECT POPULATION

6.1. Type and Number of Subjects

The study will randomize approximately 52 subjects with DLB and PDD (with approximately 34 DLB subjects) who experience frequent RBD behaviors prior to screening and meet randomization criteria (Section 6.2.3) during 1 or more qualifying night(s) in the single-blind placebo run-in period (based on a central review of video-PSG data obtained from the sleep laboratory):

Nelotanserin 80 mg - 26 subjects

Placebo - 26 subjects.

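### If the across-weeks diary and ActiGraph test is the joint 4-df treatment-by-week F, Satterthwaite df with an unstructured covariance give a true size of about 9.9% in PDD and 7.1% in DLB at nominal 5%

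*Combined protocol and SAP*

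**What the plan says.** Section 10.4.1 covers endpoints measured at "Weeks 0, 1, 2, 3, and 4 for study diary and ActiGraph assessments". It says that "between-group differences in change in mean values across weeks will be tested for the DLB patient subgroup, the PDD patient subgroup" and all patients. The analysis uses "MMRM models that include subject as a random effect, treatment arm as a between-subjects fixed effect", with week as a repeated-measures effect, "treatment arm by week interaction as a fixed effect", and background melatonin or benzodiazepine status as a covariate. On small-sample inference it says "Degrees of freedom will be calculated using Satterthwaite's formula" and "An unstructured covariance matrix will be assumed for residuals". The Statistical Methods part of the synopsis (section 2) repeats this model. Neither place names a small-sample covariance adjustment, a fallback covariance structure or a single-week contrast that decides the test.

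The objectives table in section 4 words the same diary and ActiGraph endpoints as running from Week 0 to Week 4. The nulls in section 10.1 word them as change from baseline to end of study. Section 6.1 gives the numbers: "The study will randomize approximately 52 subjects with DLB and PDD (with approximately 34 DLB subjects". That leaves about 18 with PDD. Section 5.1 gives the allocation: "Each subject will be randomized 1:1 to either nelotanserin 80 mg or matching placebo". Section 7.2 stratifies by disease type.

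**The concern.** A between-arm difference in change across five weekly means is most directly read as the 4-df treatment-by-week F test. An unstructured 5x5 covariance has 15 parameters, which in PDD come from about 18 subjects. Satterthwaite chooses denominator degrees of freedom but does not rescale the F statistic for the noise in the estimated covariance matrix. The joint test then rejects too often under the null.

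At stake are the nominal p-values for injury nights, four movement measures, four vocalization measures and the ActiGraph count. Each is secondary in DLB and is also tested in PDD and in all patients. This is not a multiplicity question, because it concerns the calibration of one test taken alone.

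The model also combines a random subject effect with an unstructured residual matrix. A random intercept adds the same constant to all 25 cells of a matrix that is already unrestricted, so the 15 + 1 = 16 covariance parameters have rank 15. The extra term is redundant and leaves the likelihood unchanged.

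**Working it through.** **The plan's own figure.** The documents give no error rate for the MMRM. The one related figure is the primary ANCOVA power of 0.62 (section 10.2). With f = 0.4 and N = 34, the noncentrality is 0.16 x 34 = 5.44. On 1 and 34 - 4 = 30 df at alpha 0.05, power is 0.617, so the stated figure reproduces. Section 10.2 states alpha 0.05 for sample size only; I assume the same level for the MMRM tests.

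**Inputs.** N = 34 for DLB, 52 - 34 = 18 for PDD and 52 for all patients (section 6.1). Five weeks give q = 5 - 1 = 4 numerator df (section 10.4.1).

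**Exact size, complete normal data.** Let v = N - 2. The Wald F on q df is Hotelling's T-squared divided by q, and under the null it follows [v/(v - q + 1)] x F(q, v - q + 1). Satterthwaite refers it to F(q, v). Hence

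size = P{ F(q, v - q + 1) > F0.95(q, v) x (v - q + 1)/v }.

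For PDD with q = 4, v = 16 and v - q + 1 = 13. The critical value F0.95(4,16) is 3.007, and 3.007 x 13/16 = 2.443. P{F(4,13) > 2.443} = 0.0991.

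| Test | PDD, N = 18 | DLB, N = 34 | All, N = 52* |
|---|---|---|---|
| 4-df treatment by week | 9.9% | 7.1% | 6.3% |
| 3-df, change from baseline at Weeks 1-4 as response | 7.6% | 6.2% | 5.7% |
| 1-df contrast | 5.0% | 5.0% | 5.0% |

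*Two-group approximation; the planned all-patients model also has disease type and its interaction with treatment.

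The 4-df size at other PDD counts is 12.2% (N = 14), 10.9% (N = 16) and 9.2% (N = 20). None of these values depends on the shape of the covariance.

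**Check by simulation.** At N = 18 with complete data and no background covariate, 100,000 null trials gave 9.9% with Satterthwaite and 4.9% with the Hotelling scaling. REML fits that include the covariate (about 2,000 trials) gave 11.0% (SE about 0.7 points), with a median denominator df of 16.0.

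**Missing weeks.** The documents give no missing-data rate, so both settings below are assumptions. Setting A has 10% of subject-weeks missing at random and correlation 0.6 (1,500 PDD runs, 800 DLB runs). Setting B has 15% dropout plus 5% intermittent missing weeks under AR(1) with 0.7, plus a heterogeneous structure with 0.8 in PDD only (about 2,000 runs each). In each PDD scenario of B, 15 of 2,004 fits did not converge and were excluded.

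| Test | PDD, A | PDD, B | DLB, A | DLB, B |
|---|---|---|---|---|
| 4-df, Satterthwaite | 16.3% | 13.9% to 14.1% | 6.6% | 8.8% |
| 4-df, Kenward-Roger | 7.9% | 7.0% to 7.3% | 4.1% | 5.8% |
| 1-df Week 4 minus Week 0, Satterthwaite | 5.9% | 5.6% to 5.8% | not run | 5.4% |

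Standard errors in A are 1.0 point (PDD) and 0.9 point (DLB) for the first row.

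**Non-normal counts.** Injury nights range from 0 to 7 per week. They were simulated as binomial with subject-specific rates and complete data. At an assumed mean of 0.5 nights per week, the 4-df test rejects about 4% (N = 18) and 4.7% (N = 34). At means of 0.8 to 0.9 it rejects 6% to 7% (N = 18). It approaches 9.5% only near 3.5 nights per week.

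**The case against.** The strongest reply is that the plan does not clearly call for the 4-df test. Sections 4 and 10.1 frame these endpoints as baseline to end of study, which is a 1-df contrast with size close to 5%. Section 10.4.1 speaks of change across weeks and includes the interaction, but never names the 4-df F as deciding. This stands, and it makes the point conditional. It does not remove it, because section 10.4.1 is where the test is specified and it names no 1-df contrast.

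Several narrower replies also stand. PDD efficacy is exploratory, and in DLB, where these endpoints are secondary, the inflation is modest. The DLB rate in setting A, 6.6%, is (6.6 - 5.0)/0.9 = 1.8 SE above 5%. The 14% to 16% range rests on assumed missingness, and the exact rates need normality. Section 10.4 defers further detail to a SAP that is not in the text available here and could name the contrast or an adjustment.

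A reader might infer that every PDD p-value for these endpoints is wrong by a factor of two to three. The documents do not support that: it requires the joint test, roughly normal data and, for the upper end, assumed missingness. A reader might also infer that the random subject effect forces Satterthwaite df to be computed from a singular information matrix. That model was not fitted, so only the redundancy is shown.

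**Conclusion.** The concern holds conditionally. If the across-weeks test is the joint 4-df treatment-by-week F with Satterthwaite df, its size at nominal 5% with complete normal data is 9.9% in PDD, 7.1% in DLB and about 6.3% in all patients. A 3-df version on change from baseline gives 7.6% in PDD and 6.2% in DLB. Missing weeks probably push PDD higher, while sparse counts may show little or no inflation. The 1-df Week 4 minus Week 0 contrast is close to nominal. The primary and key secondary analyses are ANCOVAs and are not touched. The text leaves open which test decides, and one of the readings it invites is miscalibrated in small samples. The change is worth making because it is nearly free, but it does not bear on the trial's main conclusion.

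**What to change.** In section 10.4.1 and the Statistical Methods part of the synopsis:

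1. Replace Satterthwaite with Kenward-Roger (DDFM=KR in SAS), which adjusts the covariance of the estimates, the scale of F and the df.
2. Delete the random subject effect and keep the unstructured repeated-measures covariance alone.
3. Name the 1-df Week 4 minus Week 0 treatment contrast, which sections 4 and 10.1 already describe, as the inferential test. Do this at least in PDD, where Kenward-Roger alone still leaves the 4-df test at about 7% to 8% with missing weeks.

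The cost is a wording change and one model option, with no new data, visits or subjects. The downside is slightly larger p-values for any joint test that is still reported.
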